Determining which patients, using age and arthritic burden as predictors, can benefit from labral repair is paramount for several reasons. Showing arthroscopic repair is of little or no benefit to a specific cohort can reduce the number of unnecessary surgeries performed, increase the use of conservative therapy (if validated) and reduce the interval between diagnosis and total hip replacement. Additionally, proving a benefit exists from arthroscopic repair in a certain subset of the population will substantiate the need for developing a treatment algorithm in older patients presenting with labral tears and some degree of pre-existing arthritis. Furthermore, conservative physical therapy may prove to be of equal or greater benefit than arthroscopic repair in select patients. If true, this study will be a landmark for providing the evidence needed to recommend conservative treatment as an efficacious alternative in addition to providing a foundation for future research on this topic.

II. SPECIFIC AIMS:

Specific Aim 1: To evaluate if physical therapy alone or arthroscopic labral repair and physical therapy is of greater benefit to patients presenting at age 40 with tears of the acetabular labrum.

Hypothesis 1.1: Physical therapy will result in a significant difference in mHHS scoring at 12 months when compared to baseline.

Hypothesis 1.2: Arthroscopic labral repair will result in a significant difference in mHHS scoring at 12 months when compared to baseline.

Hypothesis 1.3: Arthroscopic labral repair and physical therapy will be superior to physical therapy alone in improving function and alleviating symptoms at 12 months when compared to baseline, as judged by the mHHS.

Hypothesis 1.4: Hypotheses 1.1-1.3 will hold true at 24 months and beyond.

Hypothesis 1.5: Functional outcome scores collected at the completion of PT will not significantly differ from those collected at 12 and 24 months and beyond in the same group.

Specific Aim 2: To evaluate the effect of arthritic burden on short term outcomes following arthroscopic labral repair.

Hypothesis 2.1: In the surgical treatment group, subjects with arthroscopically proven severe osteoarthritis (Outerbridge grade 4) will do more poorly on validated outcome measures, specifically the mHHS, after arthroscopy than subjects with less severe osteoarthritis (Outerbridge grade ≤ 3).

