Our Primary Outcome is change in the modified Harris Hip Score at 12 months and 24 months. Secondary outcomes include changes in other validated outcomes measures patient satisfaction, and degree of improvement on physical exam. The influence of OA severity (Outerbridge scoring) and location of OA will also be analyzed to determine if they have an effect on the aforementioned outcome measures. Satisfaction will be assessed by an exit questionnaire (See section IV). In addition to gauging satisfaction, this questionnaire will ask subjects how they felt about their participation in the study. (See section IV)

Inclusion and Exclusion Criteria:

Inclusion criteria	Rationale
Age 40 or greater	Higher likelihood of undetectable OA on imaging
Orthopedic surgeon determines symptoms are consistent with a labral tear.	Required for treatment
Availability of hip radiographs and MRI	Needed to assess eligibility and comparison for specific aim 3
Willingness to undergo randomization and ability to understand and sign informed consent document	Ability to understand study and consent willingly

Exclusion criteria	Rationale
Unexpected pathology at the time of arthroscopy	Source of pain less likely to due dysfunction of the labrum and more likely due to aberrant extra-articular biology
Same site surgery	Complex anatomy
Contraindication to surgery or physical therapy	Cannot tolerate either treatment grouping
Alternate form of PT for greater than 6 weeks	Will negatively augment results. May affect recruitment.

Selection and enrollment:

We will enroll 122 consecutive subjects meeting the aforementioned criteria. Subjects will be randomized into conservative or surgical treatment arms. All potential subjects on the clinic schedule of the investigator will be pre-screened for eligibility based on age, clinical assessment, and previous medical history.

All eligible subjects will be approached at an outpatient clinic visit. Those who initially meet inclusion criteria will be introduced to the study and given a research consent form that they have the opportunity to take home and to review.

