The mean outcome scores of the mHHS in each treatment group at 12 months will be compared to baseline scores to assess for significant differences using paired sample t-test in SPSS 16 (SPSS, Chicago, IL). The mean outcomes scores of the mHHS between groups at 12 months will be compared using independent t-tests to assess for significant difference. We will use a Levene test to judge variance and proceed accordingly. If a statistically significant difference is detected during these analyses, we will calculate the effect size (ES) to determine how meaningful these results are outside of being statistically significant. The ES will be calculated by: [(mean mHHS score of surgical arm / mean mHHS of the conservative group) / standard deviation of the conservative group]. According to Cohen ⁵⁸, an ES <0.1 is trivial, ES of 0.1-0.3 is minimal, ES of 0.3-0.5, is moderate, and ES >0.5 is large. We will repeat the same analysis at 12 months.

Hypothesis 2.1, 2.2, and 2.3:

Diagnosis and treatment of the prearthritic and early arthritic hip has been an area of intense interest. However, our most conventional method of assessment (plain radiography) does not provide us with enough diagnostic sensitivity.⁴¹ Direct visualization on the articular surfaces in the hip is both sensitive and specific. Furthermore, emphasis is being placed on the location of arthritis as a prognostic indicator of good outcomes following hip arthroscopy. The value of arthroscopic techniques for primary

symptoms and/or prevention of OA secondary to labral tears remains unclear even though preliminary reports indicate there may be some benefit to repairing a torn labrum, even in cases of severe OA. Evaluation of arthritic change at the time of arthroscopy is important, particularly in subjects where there remains uncertainty about the efficacy of labral repair for those with articular or rim cartilage degeneration that the effects of those changes on long-term OA progression.⁵⁹

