We plan to track the effects of OA on outcomes through identification and localization of OA at the time of arthroscopy using a mapping technique (see diagram). After complete visualization of the intra-articular space, as is standard practice in hip arthroscopy, classification of any existing osteoarthritis will be done according to the Outerbridge grading scale. Using this system, we are able to categorically group subjects based on location and severity of disease. If multiple lesions are present, subjects will be characterized by the most severe grade. Furthermore, based on the data gathered through meeting hypotheses 1.1-1.4, we will subdivide primary outcome scores into four categories.⁶⁰ Category I, excellent outcomes (mHHS ≥ 90); Category II, good outcomes (mHHS ≥ 80); Category III, fair outcomes (mHHS ≥ 70), and Category IV, poor outcomes (mHHS < 70). The likelihood of outcomes based on Outerbridge grading and outcome category will be determined through odds ratios. Analysis will be carried out using Chi-squared tests. Significance is set at $P < 0.05$. Linear regression analysis will be performed to detect if any relationship exists between the severity of osteoarthritis and short-term outcome scoring.

Hypothesis 3.1:

This is an exploratory hypothesis whose assessment will no influence the other data sets. Prior work by other groups has demonstrated that evaluation of arthritic burden by conventional measures (Kellgren-Lawrence and Tonnis grading) are not indicative of the severity of arthritis found at the time of arthroscopy.⁵⁸ We will explore this phenomenon in our own cohort of subjects, specifically those in the surgical group and report our findings. We will correlate our findings for significance.

Power Analysis:

Specific Aim 1, Hypotheses 1.1-1.4: *To evaluate if physical therapy alone or arthroscopic labral repair and physical therapy is of greater benefit to patients presenting at age 40 with tears of the acetabular labrum.*

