Using the data from our retrospective review of outcomes following labral repair, a 10 point or greater difference on the mHHS as significant, and a single-tail independent t-test to evaluate the difference between means with 80% power and a 5% significance level, 35 subjects are needed to demonstrate a statistically significant difference between the average mHHS of the conservative group and surgical group. Testing of hypothesis 1.5 will be an intragroup analysis looking for a significant difference in outcome measures from the time of completion of PT (non-crossover) when compared to the same data to be collected at 12 months and 24 months. The purpose is to determine the short-term durability of the response to PT, if one is found.

70 study completers should provide us with the necessary data needed to substantiate or reject our hypothesis. There has been no prospective trial to date testing these hypotheses in the hip, but we expected a 7.3-10.3% dropout rate based on the results of a similar study in the knee. However, as of July 2018, we had 47 patients that had passed the 2-year follow-up mark, of which 5 patients were no longer in the study (combination of lost to follow-up and proceeding to total hip arthroplasty), and another 11 had yet to complete their 2-year surveys even with multiple attempts to contact them and encourage them to do so. With a yield of 31 patients out of 47, or 65.95%, we increased our sample size to 122.

Therefore, we estimate needing 122 subjects to achieve 70 study completers, in the appropriate proportion of 35 subjects per treatment arm. We enroll until reaching at least 35 subjects in each group.

The results of the MeTeOR trial in the knee show that we can expect a higher drop-out rate in the surgical group. As such, this cohort may be our limiting factor.^{40, 43, 61, 62}

Specific Aim 2. Hypotheses 2.1-2.3: *To evaluate the significance of arthritic burden on short term outcomes following arthroscopic labral repair.*

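### Two primary time points, 12 and 24 months, share one 5% level with no lead, testing order or success rule, and the 24-month comparison is not written

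*Combined protocol and SAP*

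**What the plan says.** - **Primary outcome** (Section III, Study Overview and the paragraph after it): "Our Primary Outcome is change in the modified Harris Hip Score at 12 months and 24 months". Neither time is put first. Hypothesis 4.1 also speaks of primary outcome scores at 12 and 24 months, so the pairing is not a stray phrase.
- **Hypotheses** (Section II). Hypothesis 1.3 is the between-group claim: "Arthroscopic labral repair and physical therapy will be superior to physical therapy alone in improving function and alleviating symptoms at 12 months". Hypothesis 1.4 extends it: "Hypotheses 1.1-1.3 will hold true at 24 months and beyond".
- **Analysis** (Section V, Hypothesis 1.1-1.4). Paired t-tests within each arm and an independent t-test between arms are described at 12 months. The paragraph ends: "We will repeat the same analysis at 12 months".
- **Level and power** (Section V, Power Analysis). One statement is headed "Specific Aim 1, Hypotheses 1.1-1.4" and specifies a "single-tail independent t-test to evaluate the difference between means with 80% power and a 5% significance level". The sentence that derives 35 subjects names no time point. A threshold of P < 0.05 also appears in the Aim 2 analysis text.
- **Not stated anywhere:** a lead time point, a division of the 5%, a testing order, or a rule on whether one or both time points must succeed.

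**The concern.** With two primary time points and no decision rule, a result that is significant at one time and not the other could be reported as a positive primary finding whichever time it came from. In that case the declared 5% would describe each test and not the trial's primary claim.

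The analysis text is where a reader would look to settle this, and it does not help. It describes the comparison at 12 months and then repeats it at 12 months. As printed, one of the two declared primary time points has no analysis at all. That gap needs closing whatever view is taken on multiplicity.

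The setting adds weight. Section VIII says that there are no blinded treatment groups and no data monitoring board, and that data are reviewed on a running basis. The 12-month comparison could therefore be known before the 24-month data are complete.

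**Working it through.** **1. The plan's own figure.** The documents state no overall type I error for the two time points, so there is none to reproduce. The stated figure is 35 completers per arm, for a 10-point difference, one-sided 5% and 80% power. No SD is given, so 35 cannot be confirmed. It can only be inverted, with n = 2(z0.95 + z0.80)² SD² / δ²:

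SD = δ√(n/2) / (z0.95 + z0.80) = 10 × √17.5 / (1.645 + 0.842) = 41.83 / 2.487 = 16.8.

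The figure is thus what a single test at one-sided 5% would need if the SD were about 16.8. It contains no allowance for a second primary test.

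**2. Error if success at either time counts.** Let Z12 and Z24 be the between-group test statistics, each standard normal when there is no treatment effect, with correlation r. With each tested one-sided at 5%:

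error = P(Z12 > 1.645 or Z24 > 1.645) = 1 − Φ2(1.645, 1.645; r),

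where Φ2 is the bivariate normal distribution function. The two-sided version uses |Z| > 1.960. The documents give no r, so it is an assumption and a range is shown.

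| r (assumed) | one-sided | two-sided |
|---|---|---|
| 0 | 9.75% | 9.75% |
| 0.3 | 9.3% | 9.5% |
| 0.5 | 8.8% | 9.1% |
| 0.7 | 8.0% | 8.4% |
| 0.8 | 7.5% | 7.8% |
| 0.9 | 6.8% | 7.0% |
| 0.95 | 6.3% | 6.5% |

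The first row is 1 − 0.95² = 0.0975.

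**3. Error under other rules.**
- Both must succeed: the event lies inside each single rejection region, so its probability is at most 5%.
- 24 months tested only after success at 12 months: a false claim when there is no effect requires a false 12-month rejection, so the error is 5%. If the 12-month effect is real and the 24-month effect is not, the only possible false claim is the 24-month one, again at most 5%.

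**4. Price of the alternatives.** Splitting to one-sided 0.025 at each time holds the overall error at 3.9 to 4.9% (r from 0.8 to 0). With the implied SD of 16.8, power at each time point becomes Φ(2.487 − 1.960) = Φ(0.527), or 70%. Restoring 80% needs 2 × (1.960 + 0.842)² × (1.682)² = 44.4, so 45 per arm. At the observed 2-year yield, 122 × 31/47 = 80.5 completers, or about 40 per arm, which falls short of 45. The fixed sequence leaves the 12-month power unchanged.

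**The case against.** The strongest reply is that the plan never says either time point suffices. It joins the two times with *and*. Hypothesis 1.4 can be read as durability: the 12-month finding is expected to persist. On that reading 24 months matters only after 12 months has succeeded, and the error is not inflated. It is also fair to say that a 24-month test at the full 5% is an inference from Hypothesis 1.4 and the shared power heading, because Section V writes no such test.

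Both points stand against a stronger reading. A reader might infer that the trial's false-positive rate is 7.5 to 9% instead of 5%. The documents do not support that as a fact. It needs an either-one-counts rule that is not stated and a correlation that is not given.

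The reply does not remove the gap. Hypothesis 1.4 states an expectation and not a testing order, and the primary-outcome sentence makes both times primary without condition. If a sequence or a both-must-succeed rule is intended, it is not written.

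A reader might also infer that the sample size belongs to 12 months, and that 12 months therefore leads already. The documents point the other way. The power heading includes Hypothesis 1.4, and the increase to 122 rests on the 2-year yield (31 of 47).

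**Conclusion.** The plan declares two primary time points under one 5% level, gives no rule for combining them, and does not write the 24-month comparison. Those facts rest on the text alone.

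The size is conditional. If either time point may carry the primary claim at 5% each, the family-wise error is about 6 to 10% (6.3 to 9.75% one-sided for r from 0.95 to 0). It is 7.5 to 8.8% one-sided, or 7.8 to 9.1% two-sided, for r from 0.8 to 0.5. If both must succeed, or 24 months is gated on 12, it does not exceed 5%. The figures cover only the between-group comparison. They leave out the within-arm tests of Hypotheses 1.1 and 1.2 and any test after 24 months. The plan should be amended so that the level no longer depends on how it is read.

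**What to change.** 1. Name the 12-month between-group mHHS comparison as the lead primary test. The basis is Hypothesis 1.3 and the t-test already described in Section V, not the sample size.
2. Test the 24-month comparison at the full 5% only if the 12-month test is significant. This turns Hypothesis 1.4 into an explicit second step.
3. Treat follow-up after 24 months as descriptive.
4. Change the last line of the Hypothesis 1.1-1.4 analysis to 24 months.
5. Date the amendment before any between-group comparison is made. If one has already been made, say so in the report.

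**Cost.** The text change is small and takes no power from the 12-month test. Two costs should be stated openly. First, if 12 months fails there is no formal 24-month claim, although enrolment was raised on 2-year yield. Requiring both time points, or leading with 24 months, would also hold 5%, so this is a choice the sponsor must own. Second, timing: 47 patients had passed two years by July 2018, treatment groups are not blinded, data are reviewed continuously, and the cover page cites a 2021 continuing review. A lead time point chosen after outcomes by arm have been seen does not by itself secure the 5% level, which is why the date or the disclosure matters.

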[name] and [name] were investigators in a similarly designed multicenter trial involving meniscal tears in the knee.⁴³ In that recently published study, once enrolled, the patient retention rate was approximately 90%. We believe we will have similar success over the course of this study. Nevertheless, procedures will be in place to aid in maintaining subject participation over the course of the study. Outcome measures collected around formal visits can be collected remotely. Subjects can receive the surveys via email sent through REDcap. Study staff will conduct reminder phone calls around data collection time points.

IV. STUDY PROCEDURES:

Enrolled subjects will complete surveys around normal clinic visit intervals. Subjects will continue receiving surveys around their normal postoperative clinic visits until they request to stop receiving them. We are interested in long-term outcomes for these treatment arms, so we hope to collect patient-reported outcome measures for several years after randomization. These surveys can be completed remotely or at clinic visits. Follow up/reminder calls will be conducted to ensure subjects complete surveys.

Medical History:

The medical record may be reviewed for relevant medical history, imaging, physical exam, and surgical procedure from the subject's operative note, imaging, or clinic visit notes.

Patient-Reported Outcome Measures (PROMs) Surveys:

Pain/Physical Function:

Modified Harris Hip Score (mHHS): The MHHS is a validated condition specific outcome instrument that is used widely after hip arthroscopy. The eight questions measure domains of pain, gait function, and functional activities. Scores range from 0 (poor) to 100.1 (ideal).^{45,46}

The Lower Extremity Function Scale (LEFS): The LEFS is a 20 item validated outcome measure that is commonly used by physical therapists to initially evaluate and subsequently monitor patient progress through the course of a rehabilitation program. The minimum level of detectable change is 9 points.⁴⁷

Hip Outcome Score (HOS): The HOS is composed of the activities of daily living (HOS-ADL) subscale and the sports (HOS-sports) subscale. The HOS-ADL subscale contains 19 items pertaining to basic daily activities, and the HOS-sports subscale contains 9 items pertaining to higher-level activities, such as those required in athletics. In addition to the 5 potential responses, ranging from "unable to do" to "no

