difficulty," a response of "not applicable" is an option to allow subjects to designate that something other than their hip problem limits their activity. Use of the HOS is supported for individuals with labral tears. Importantly, this includes individuals who underwent arthroscopic surgery, as well as those who did not.⁴⁸ A score change beyond 3 points represents a change beyond measurement error for the HOS-ADL and HOS-sports subscales. An increase in the score above 9 points and 6 points represents a meaningful increase for the HOS-ADL and HOS-sports subscales, respectively.⁴⁹

The Nonarthritic Hip Score (NAHS): The NAHS is a validated, self-administered 20-item questionnaire designed to assess non-arthritis hip pain in patients with high activity demands and expectations.⁵⁰

International Hip Outcome Tool-33 (iHOT-33): Measure health related quality of life. The iHOT-33 includes 33 questions or items, each answered by marking a visual analog scale between 2 anchor statements. This can be done on a paper form (with a 100-mm scale) or as part of a computer-based system. The total score is calculated as a simple mean of these responses ranging from 0 to 100, with 100 representing the best possible quality-of-life score. It is most suited for research purposes.⁵¹

Psychiatric/Psychological Measures:

Short Form 36 (SF-36): The SF-36 is a self-administered questionnaire consisting of 36 items, requiring 5-10 minutes to complete. The 36 items generate a profile of scores across eight dimensions of health: physical functioning (10 questions), social functioning (two questions), role limitations (physical problems) (four questions), role limitation (emotional problems) (three questions), mental health (five questions), vitality (four questions), pain (two questions), general health (five questions). One question addressing health change (transition) is not scored nor represented in the eight dimensions.⁵³ SF-36 appears to be a valid instrument, responsive to changes in health status over time among unintentionally injured adult people. Thus it may be possible to use the SF-36 to describe changes in health due to injury. The applicability of this or similar measures for injured children remains to be established.⁵⁴

Exit Questionnaires:

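### The plan gives the eight-question mHHS no priority and no stand-alone fallback, although 11 of 42 subjects still in the study (26%) had 2-year surveys outstanding in July 2018

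*Combined protocol and SAP*

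**What the plan says.** Section III of the combined protocol and SAP (Study Overview, outcome paragraph) defines the endpoint: "Our Primary Outcome is change in the modified Harris Hip Score at 12 months and 24 months". Section IV, under the PROMs surveys, describes the mHHS: "The eight questions measure domains of pain, gait function, and functional activities". The same list contains longer instruments: "The LEFS is a 20 item validated outcome measure"; "The HOS-ADL subscale contains 19 items pertaining to basic daily activities, and the HOS-sports subscale contains 9 items"; "The NAHS is a validated, self-administered 20-item questionnaire". It also has iHOT-33 with 33 items and SF-36 with 36. The Study Overview names five of these measures and leaves out SF-36.

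Section III, Study retention procedures, allows remote collection and e-mailed REDCap surveys, and then says: "Study staff will conduct reminder phone calls around data collection time points". The opening of Section IV gives the purpose of the calls as getting the surveys completed. No section ranks mHHS above the other instruments, defines a minimum dataset, or provides for taking mHHS during a call.

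Section V, Power Analysis for Specific Aim 1, reports the position in July 2018. Of 47 subjects past 2 years, 5 were no longer in the study and "another 11 had yet to complete their 2-year surveys even with multiple attempts to contact them and encourage them to do so". The yield of 31 of 47 is given as the reason for raising the sample size to 122.

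**The concern.** Most of the 2-year shortfall reported in Section V is survey non-completion by people still in the study, not exit from it. That is the kind of missing data a follow-up procedure can try to reduce. The plan's remedy is to enrol more subjects. If those who respond differ from those who do not, and differ by another amount in the other arm, a larger sample gives a more precise estimate of the same biased difference. Section V compares mean mHHS by t-tests and names no method for missing scores, so subjects without a score drop out of the comparison. It also expects more dropout in the surgical group, so unequal loss between arms is foreseen. A short request for the primary endpoint alone is an obvious step that the plan does not take.

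**Working it through.** **Inputs.** Item counts come from Section IV. The counts 47, 5, 11, 31, 122 and the 70 required completers come from Section V, Power Analysis. The number recovered, r, is an assumption from 0 to 11, because the documents give no basis for a narrower range.

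**1. The plan's own yield.** 47 − 5 − 11 = 31, and 31/47 = 65.96%. The plan prints 65.95%, so the figure reproduces apart from truncation.

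**2. Share of the shortfall that is non-completion.**
- Still in the study: 47 − 5 = 42, and 42/47 = 89.4%.
- Outstanding among them: 11/42 = 26.2%.
- Share of all non-completers: 11/(5 + 11) = 11/16 = 69%.

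**3. Size of the survey set.**
- Study Overview list (mHHS, LEFS, HOS, NAHS, iHOT-33): 8 + 20 + (19 + 9) + 20 + 33 = 109 items.
- With SF-36: 109 + 36 = 145 items.
- mHHS share: 8/109 = 7.3%, or 8/145 = 5.5%.

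**4. Why a larger N does not remove the bias.** In one arm let m be the fraction missing and g the responder mean minus the non-responder mean. The true arm mean is (responder mean) − m·g, so responders overstate it by m·g. With equal m in both arms, the bias in the arm difference is m × (g in surgery − g in physical therapy). N does not appear. As an illustration only, suppose the two gaps differ by 10 points. With m = 16/47 = 34.0%, the bias is 3.4 points, against the 10-point difference used for planning. This holds at any enrolment.

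**5. What recovery could give.** Yield = (31 + r)/47. The 47 subjects were already past 2 years in July 2018, and the cover page carries a February 2021 review date, so their 2-year scores cannot now be obtained. Completers out of 122 are therefore 31 + 75 × yield, with 75 = 122 − 47. The last column keeps the illustrative 10-point difference in gaps, assumes it is unchanged among those still missing, and applies to the subjects who can benefit.

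| r of 11 | 2-year yield | Completers of 122 | Missing, m | Illustrative bias |
|---|---|---|---|---|
| 0 | 66.0% | 80.5 | 34.0% | 3.4 |
| 3 | 72.3% | 85.3 | 27.7% | 2.8 |
| 8 | 83.0% | 93.2 | 17.0% | 1.7 |
| 11 | 89.4% | 98.0 | 10.6% | 1.1 |

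The first row already exceeds the 70 completers required. The gain is in how well responders represent those randomised, more than in reaching the target number.

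**The case against.** Several stronger readings are tempting, and the documents support none of them.

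- A reader might infer that the 2-year mHHS is lost in 11 subjects. Section V says only that the surveys were outstanding at one date. It gives no data by instrument, and nothing on 12 months, where Hypotheses 1.1 to 1.3 are tested.
- A reader might infer that survey length caused the non-return. No section says so, or says that all instruments go out as one package each time. mHHS is also the first instrument described.
- A reader might infer that the calls would have recovered the scores. Repeated contact had already failed, and the text does not say whether anyone was reached. Recovery of zero is possible.
- A reader might set the retention statement, "In that recently published study, once enrolled, the patient retention rate was approximately 90" per cent, against the 66% yield. These are different quantities. Retention here was 42/47 = 89%, in line with that statement, and Section V already re-plans on the yield.
- A reader might call this the largest threat to the primary comparison. The plan also allows crossover from 6 weeks and removes surgical subjects with unexpected pathology. Nothing here ranks missing mHHS above either.

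It is also fair to say that telephone collection is unspecified rather than excluded, that subjects are seen in clinic, and that REDCap reports missing data.

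The strongest point concerns the remedy. Only late responders would be telephoned, so mode is tied to lateness and a mode flag cannot fully separate the two. Staff-administered scoring in an unblinded trial could also introduce bias if non-return differs by arm. This stands, and it shapes the fix. What the objections leave intact is the absence of any priority or fallback for the primary endpoint, and the 11 of 42.

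**Conclusion.** The point holds as a gap in procedure. The plan neither prioritises mHHS nor provides for collecting it alone, its calls are described only as reminders, and 26% of subjects still in the study had outstanding 2-year surveys at the one snapshot reported. Raising enrolment to 122 does not address the bias this may carry.

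The possible gain is a 2-year yield of 66% to 89%, depending wholly on the assumed recovery of 0 to 11 of 11. At 3 to 8 recovered, it is about 85 to 93 completers of 122 against about 80. Those counts assume that all 75 later subjects can still benefit and that the July 2018 pattern continues. The documents do not say how many 12- or 24-month windows are still open, so the real gain may be smaller. The change is worth making because it costs little, not because its benefit is established.

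**What to change.** In Section III, Study retention procedures, with a matching line in Section IV:

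- Put mHHS first in every REDCap survey and save it separately, so that a partly completed set still yields the primary endpoint.
- Fix a day within each visit window. If the set has not been returned by then, use the existing reminder message or call to request only the eight mHHS questions: a short self-completed link first, then telephone.
- Use one script in both arms and, where feasible, callers from existing staff who do not know the arm.
- Record mode and date of completion, and run a sensitivity analysis that excludes telephone or late responses.
- Apply this only to subjects whose 12- or 24-month window is open. Do not seek 2-year scores from subjects already past it.
- Report mHHS completeness by arm at 12 and 24 months, so that the scale of the problem is known for the endpoint itself.

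The cost is a few minutes on calls already made, a REDCap reorder and an IRB amendment. The main downside is a possible mode effect, partly confounded with late response, which the sensitivity analysis can describe but not remove. The retention statement in Section III can stay, since it concerns a different quantity from the survey yield.
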